- Has a disease or takes medication that, in the opinion of the investigator, could interfere with the assessments of safety, tolerability, or efficacy or prevent the individual from completing the study. Female subjects of childbearing potential not on adequate contraception methods in the opinion of the investigator
 - If the female is childbearing, she must agree to use appropriate contraceptive measures for the duration of the study and for one month afterwards. Medically acceptable contraceptives include: (1) surgical sterilization (such as tubal ligation or hysterectomy), (2) approved hormonal contraceptives (such as birth control pills, patches, implants, or injections), (3) barrier methods (such as condom or diaphragm) used with a spermicide, or (4) an intrauterine device (IUD). Contraceptive measures such as Plan B™, sold for emergency use after unprotected sex, are not acceptable methods for routine use. If the female does become pregnant during this study she must inform the study physician immediately.
- Has a significant risk of suicide according to Columbia Suicide Severity Rating Scale (CSSRS) or in the clinical judgment of the investigator
- History of suicide attempt in the previous 12 months
- MDD with postpartum onset, psychotic features or seasonal features
- Hamilton Anxiety Scale (HAM-A) baseline score ≥ 24
- Failure of ≥ 3 adequate trials of different antidepressants for the current episode of MDD
- ≥ 3 episodes major depression in previous 12 months or ≥ 8 lifetime episodes of MDD
- Current or previous use of an atypical or typical antipsychotic agent for augmentation of major depression or treatment of psychotic depression, mania psychosis, or agitation. Previous use of antipsychotics for insomnia will be permitted.

V. STUDY PROCEDURES

A. Blinding and Controls:

The study will be rater blinded, randomized, parallel study. Patients will be randomized in 1:1 ratio to levomilnacipran ER switch arm or adjunctive quetiapine arm. Subjects will be instructed not to discuss any clinical issue with the blinded rater. The blinded rater will be specifically instructed to perform specified ratings only and not to address or ask any other study related questions.

B. Drugs, Dosages, and Regimens:

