All allowed concomitant medications will be unchanged throughout the study. Other psychotropic medications will require a 2-4 week washout, depending on the half life of the applicable medication after the subject is deemed eligible after the screening visit. Subjects will be monitored weekly by phone for side effects or symptom worsening during the taper. Subjects randomized to the Levomilnacipran switch arm will have their SSRI tapered over 2-4 weeks after they are determined to be eligible for the study to avoid risk of discontinuation syndrome. Subjects randomized to the adjunctive quetiapine arm will have their pre-existing antidepressants continue unchanged at baseline. A flexible dose regime of levomilnacipran ER 40-120 mg/d mg per day will be followed with the FDA approved package insert. Initial titration dose will be 20 mg/d Days 1-2, increasing to 40 mg/d from Days 3-7 in week 1, flexibly dosed between 40 mg/d - 120 mg/d week 2 to week 8. FDA approved package insert guidelines will be followed for adjunctive quetiapine dosing. Adjunctive quetiapine will be started at 50 mg/d Day 1-2, increasing to 150 mg/d Days 3-7 and flexibly dosed between 150-300 mg/d week 1-8. Patients who cannot tolerate the higher dose of levomilnacipran ER or quetiapine will have their dose reduced to the lower dose per the investigator's judgment. At the end of the 8-week trial, subjects in each group will have 1-week taper of study drug. A week 9 follow up safety assessment will be performed. Subjects will be told how to safely restart their

prior medication or can be provided with a referral for continued treatment as needed.

Any new medication started during the study will be evaluated by the investigator to determine its effect on study integrity and subject safety. Subjects and primary raters will be blinded to study drug and doses.

Arm I: Levomilnacipran ER flexible dose regime (40-120 mg/d): titration dose of 20 mg po once a day from days 1-2, then 40 mg po once a day, 80mg po once a day or 120 mg once a day.

Arm II: Quetiapine flexible dose regime: 50 mg po once a day as initiating dose, 150 mg po once a day (during the period that the subjects will be titrated on 150 mg; they will be given 1-50mg tab and 1-100 mg tab with instructions to be taking once per day) (, then 300 mg po once a day.

C. Visit specific procedures and sequence:

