This is an 8-week trial with a 1 week (week 9) safety follow up visit. Visits will be planned to occur at the screening visit and weeks 0, 1, 2, 3, 4, 6, 8 and 9.

The following activities and/or assessments will be performed at/during the Screening visit (Week -4 to Week 0):

- Obtain written informed consent prior to performing any of the formal screening procedures.
- Administer the M.I.N.I
- Administer the C-SSRS, MADRS, ASEX, HAM-D, HAM-A, DSST, CGI-S, RVLTL, Spontaneous Reported AEs and Sheehan Disability
- Record demographic information
- Obtain medical and surgical and psychiatric history
- Record prior and concomitant medications
- Record vital signs (temperature, heart rate, supine and orthostatic blood pressure), body height and body weight
- Perform a complete physical examination
- Perform a 12-lead ECG

- Collect blood and urine samples for evaluation of standard laboratory safety test (chemistry, hematology, and urinalysis)
- Assess all applicable inclusion and exclusion criteria
- Schedule the baseline visit for those subjects that do not require washout of prohibited medications
- Subjects requiring washout of prohibited medication will be provided washout requirements
 - Subjects in adjunctive quetiapine arm will be permitted to continue their pre-existing antidepressants if FDA approved for depression; if not FDA approved, they will be switched to an FDA approved medication for the duration of the study but will undergo washout of other prohibited medications
- Provide instructions on washout of prohibited medication(s), including the duration of the washout period (if needed)
- Assess for and record AEs and concomitant medications

Once potential eligibility is confirmed, the investigator, or a person designated by the investigator, will contact the subject by telephone at or during the Randomization/Baseline (Week 0):

- Determine appropriate duration of the washout period of prohibited medication(s), taking into account any labeling requirements for tapering of medication dose(s), as well as the minimal washout requirements

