 - Weekly phone calls will include a Symptom Checklist, consistent with symptoms of Major Depression, suicidal risk and adverse events, which the Study Coordinator will review with the subject. Any potential concerns will be reviewed with the subject. Any potential concerns will be discussed with the PI and appropriate interventions for subject safety will be planned. The same symptom checklist and monitoring plan for the subjects will be used at the Duke and the non-Duke site.
- Assess all applicable inclusion and exclusion criteria

- Administer the C-SSRS, MADRS, ASEX, HAM-A, DSST, CGI-S, RVLTL, AES, Spontaneous Reported AEs and Sheehan Disability
- Assess for and record AEs and concomitant medications
- Dispense study medication

The following activities and/or assessments will be performed at Weeks 1 through Weeks 6:

- Assess for and record AEs and concomitant medications
- Administer the C-SSRS, MADRS, ASEX, HAM-A, DSST, CGI-S, RVLTL, AES, Spontaneous Reported AEs and Sheehan Disability
- Collect study medication and review medication compliance
- Dispense study medication

The following activities and/or assessments will be performed at Week 8: End of Study or Early Termination:

- Assess for and record AEs and concomitant medications
- Collect study medication and review medication compliance
- Record vital signs (temperature, heart rate, supine and orthostatic blood pressure), and body weight
- Collect blood and urine samples for evaluation of standard laboratory safety tests
- Administer the C-SSRS, MADRS, ASEX, HAM-A, DSST, CGI-S, RVLTL, AES, Spontaneous Reported AEs and Sheehan Disability
- Perform a 12-lead ECG

The following activities and/or assessments will be performed at the Week 9/ Safety Follow-Up Visit:

- Assess for and record AEs and concomitant medications
- Administer the C-SSRS, Spontaneous Reported AEs and the DSST

After all study assessments has been completed or if the participant completes an early term visit, the participants will be referred back to their outpatient treating physician for

psychiatric care. Participants who are uninsured will be referred to Lincoln Community Health Center or Durham Access. Results of the subject's participation will not be available to the subject before they return to their treating doctor.

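### Randomisation is placed both before the switch-arm SSRI taper and at Week 0; on the first order, the Week 0 eligibility recheck can remove assigned switch patients before their first dose

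*Combined protocol and SAP*

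**What the plan says.** **Exclusions (IV.D).** Two of the criteria could be met because of SSRI withdrawal: "Hamilton Anxiety Scale (HAM-A) baseline score ≥ 24" and "Has a significant risk of suicide according to Columbia Suicide Severity Rating Scale (CSSRS) or in the clinical judgment of the investigator". The first uses the word baseline without naming a visit.

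**Taper (V.B).** "Subjects randomized to the Levomilnacipran switch arm will have their SSRI tapered over 2-4 weeks after they are determined to be eligible". For the other arm, "Subjects randomized to the adjunctive quetiapine arm will have their pre-existing antidepressants continue unchanged at baseline". The section gives avoidance of a discontinuation syndrome as the reason for tapering, and it arranges weekly telephone monitoring for symptom worsening.

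**Screening list (V.C, Week -4 to Week 0).** It contains an instruction specific to one arm: "Subjects in adjunctive quetiapine arm will be permitted to continue their pre-existing antidepressants if FDA approved for depression".

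**Week 0 list (V.C).** It includes "Assess all applicable inclusion and exclusion criteria", then "Administer the C-SSRS, MADRS, ASEX, HAM-A, DSST, CGI-S, RVLTL, AES, Spontaneous Reported AEs and Sheehan Disability", and ends with dispensing of study drug. The Schedule of Events also marks eligibility at both Screening and Week 0, and labels Week 0 as randomisation and baseline.

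**Statistical Evaluation, B and C.** Randomisation follows the coordinator's determination of eligibility. The ITT group needs receipt of study drug and a post-baseline efficacy assessment. The safety population needs study drug and a post-baseline safety assessment.

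**The concern.** Coming off the SSRI is part of the switch strategy. If patients are assigned first, tapered in one arm, and then tested again against entry limits, a switch patient can be lost because of an effect of the assigned strategy. The quetiapine arm has no matching exposure.

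Such a patient has no study drug and no later MADRS, so the analysis sets as defined cannot bring the patient back. Both the efficacy comparison and the tolerability comparison, which together form the primary objective, would then rest on groups that randomisation no longer makes comparable. With 30 per arm, a handful of such losses matters.

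**Working it through.** **Step 1. The two orders.**

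| | Order A | Order B |
|---|---|---|
| Support | V.B (taper in subjects already randomised to the switch arm); arm-specific instruction in the V.C Screening list | Schedule and V.C label for Week 0; Randomization Method (eligibility, then randomisation) |
| Sequence | Eligible, assigned, taper in one arm, Week 0 recheck, first dose | Eligible, Week 0 check, assigned, first dose |
| Does the recheck remove assigned patients? | It can | No |
| Conflict | Week 0 is not the randomisation visit | No arm-specific taper is possible before Week 0 |

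The Screening window of up to four weeks is long enough for a 2-4 week taper, so Order A is workable. The Randomization Method alone does not settle the matter: it requires only that eligibility comes before randomisation, and V.B also puts the taper after eligibility.

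**Step 2. What can be rechecked at Week 0.** HAM-A and C-SSRS are scheduled at Week 0. HAM-D, laboratory tests, ECG, vital signs and the MINI are not, so the HAM-D entry threshold of 14 is not measured again.

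**Step 3. Analysis sets.** Under Order A, a patient who fails at Week 0 is randomised but has no study drug and no post-baseline assessment. That patient is in neither the ITT group nor the safety population.

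**Step 4. How many might reach 24.** The plan has no figure to reproduce. Every input here is an assumption except the limit of 24 (IV.D) and 30 per arm (IV.A).

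- Screening score X: normal, mean m = 15 or 17, SD 5, kept if below 24.
- Retest SD s = 2.5 or 3.5; taper rise d = 0, 2 or 4 points.
- Additive model: W = X + e + d, with e of SD s and whole-number scores. The Week 0 variance grows to 25 + s².
- Stable-variance model: W = m + r(X − m) + e + d, with r = √(1 − (s/5)²), which is 0.87 or 0.71.
- Share removed = 1 − P(X < 24 and W < 24) / P(X < 24).

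| Rise d | Additive | Stable variance | Combined | Of 30 |
|---|---|---|---|---|
| 0 | 3-8% | 2-5% | 2-8% | 1-2 |
| 2 | 9-16% | 5-11% | 5-16% | 2-5 |
| 4 | 17-28% | 13-22% | 13-28% | 4-8 |

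The last column is 30 times the combined share, for example 30 × 0.13 = 3.9 and 30 × 0.28 = 8.4. In the additive model at a rise of 4, kept switch patients average 1.2-1.5 points below all eligible patients on Screening HAM-A. An arm with no rise averages 0.2-0.4 below, so the gap is roughly 1 point.

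**Step 5. What that could do to the comparison.** Suppose a share q with the highest Week 0 scores is removed from one arm and none from the other. Let ρ (assumed 0.2-0.6) be the absolute correlation of that score with the outcome. The spurious difference in outcome SDs is ρ × φ(z) / (1 − q), with z the upper q point of the normal.

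- q = 0.10: 0.1755 / 0.90 = 0.195, giving 0.04-0.12 SD; two-sided type I error about 0.05-0.07.
- q = 0.20: 0.280 / 0.80 = 0.350, giving 0.07-0.21 SD; about 0.06-0.12.
- q = 0.30: 0.348 / 0.70 = 0.497, giving 0.10-0.30 SD; about 0.06-0.18.

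This shows size only. The sign depends on the sign of the correlation, which the documents do not give.

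**The case against.** The best defence is Order B: Week 0 is labelled the randomisation visit, and the Randomization Method assigns after eligibility. On that order no assigned patient is lost to the recheck. This stands as a limit on the point, but it does not dispose of it, because V.B and the Screening list contradict that order and a site could follow either.

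Other parts of the defence also stand.

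- V.B does not say that the taper ends before the first dose. Completion by Week 0 is an inference from the list order and the window.
- Only applicable criteria are rechecked. A reader might infer that the whole entry list is applied again; the Week 0 assessments do not allow that.
- No text says outright that an assigned patient with a Week 0 HAM-A of 24 or more is removed. It follows from the criterion, the recheck, and the rule under Study Discontinuation/Termination (item 2) for conditions that are exclusion criteria.
- A reader might infer that only the switch arm can lose patients. Ordinary variation, washout of other drugs, or a change from a non-approved antidepressant could also remove quetiapine patients. Only worsening off the taper is confined to one arm.
- The additive model inflates Week 0 variance. The stable-variance results are lower, and the combined range covers both.

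**Conclusion.** The documents contain two incompatible orders of randomisation, taper and eligibility check. On the order in V.B, the Week 0 recheck is a selection made after assignment and after a treatment change in one arm, and the ITT and safety definitions cannot recover those removed. That is a real weakness and worth correcting. It is conditional on that order being the one followed.

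A reader might go further and conclude that the plan biases the result in favour of switching. The documents do not support that. Removing patients who worsened could leave a better-prognosis switch arm, but it also removes high Week 0 scores with the most room to fall. The selection is on HAM-A, while the outcome is MADRS change adjusted for baseline MADRS. Loss of comparability is established on this order; its direction is not.

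The size, from about 1 to about 8 of 30 switch patients for rises of 0 to 4 points, rests wholly on the assumed mean, SD, retest variation and taper effect.

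**What to change.** 1. Reconcile V.B, V.C (Screening and Week 0 lists), the Randomization Method and the Schedule to one order of events.
2. In IV.D, tie the HAM-A eligibility limit to the Screening, pre-taper score. State that eligibility for entry is confirmed before assignment is made.
3. In the Plan of Data analysis, define the efficacy and safety sets to count every randomised subject in the assigned arm from randomisation. Use the pre-taper screening MADRS as baseline. Report the number of pre-dose losses, with reasons, by arm.
4. State how randomised subjects with no post-baseline MADRS are analysed. Last observation carried forward has no post-baseline value to carry for them.

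Clinical safety stopping before or after first dose, including for suicide risk, stays with the protocol's own rules, and no change to them is proposed here. The exclusions in IV.D, the termination rule at the end of V.C, and item 2 of Study Discontinuation/Termination must be reconciled on how they apply to subjects already assigned.

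The cost is mainly wording: HAM-A, C-SSRS and MADRS are already taken at Screening. A few subjects with higher Week 0 anxiety would stay in the trial, and some randomised subjects would have missing outcomes that the analysis must handle.

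### The order of randomization, SSRI taper and baseline MADRS is inconsistent; if the taper falls between assignment and Week 0, the primary baseline is a post-randomization value altered mainly in one arm

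*Combined protocol and SAP*

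**What the plan says.** Section V.B (Drugs, Dosages, and Regimens) ties the SSRI taper to the arm: "Subjects randomized to the Levomilnacipran switch arm will have their SSRI tapered over 2-4 weeks", beginning once eligibility is settled. For the other arm, "Subjects randomized to the adjunctive quetiapine arm will have their pre-existing antidepressants continue unchanged at baseline". The same section adds, without limiting it to an arm, "Other psychotropic medications will require a 2-4 week washout". Levomilnacipran begins straight away: "Initial titration dose will be 20 mg/d Days 1-2".

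In section V.C, the Screening list covers Week -4 to Week 0 and already contains an arm-specific instruction: "Subjects in adjunctive quetiapine arm will be permitted to continue their pre-existing antidepressants if FDA approved for depression". A rule for anyone whose current drug lacks that approval comes next: "if not FDA approved, they will be switched to an FDA approved medication for the duration of the study". The instruction ends by saying that this arm's subjects may keep an antidepressant "but will undergo washout of other prohibited medications".

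The Week 0 list in V.C includes the telephone contact about washout, a recheck of the entry criteria, the MADRS and the first dispensing. The Schedule of Events gives randomization and baseline a single Week 0 column. MADRS and HAM-A are scheduled at screening and at Week 0, with nothing between.

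Statistical Evaluation, part B, places randomization after the coordinator's eligibility decision but does not place it relative to the taper. The primary outcome is the MADRS change from baseline. Part C allows repeated measures ANOVA or an ANCOVA with baseline MADRS as a covariate.

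**The concern.** Randomization balances the arms on anything measured before it. A baseline measured after assignment has that protection only if nothing arm-specific has happened in between. Here a 2-4 week SSRI withdrawal is planned for one arm, and the plan leaves open whether it comes before or after the Week 0 MADRS.

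If it comes before, a temporary rise in MADRS during the taper lifts the starting point of the switch arm. Its later resolution then looks like improvement on levomilnacipran. Adjusting for the shifted score does not fully undo this, because ANCOVA removes the shift only to the extent that baseline fails to predict Week 8. The Week 0 recheck of entry criteria, including the HAM-A limit, would also fall after assignment.

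If the taper comes after, the baseline is sound. What then needs stating is that the switch arm is still partly on an SSRI for up to 2-4 of the 8 treatment weeks.

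**Working it through.** **Step 1. Which orders does the text allow?** The plan gives no figure on this point, so the sections are compared first.

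- *Taper before assignment:* not possible as written, because only one arm is tapered.
- *Taper between assignment and Week 0 (order A).* For: V.B speaks of subjects already randomized. The Screening list instructs one arm by name, and its reference to other prohibited drugs suggests that the switch arm's SSRI is washed out in the same window. Weekly phone monitoring also fits better before Week 0, since Weeks 1 to 4 already have visits, although those calls also serve the washout of other drugs in either arm. Against: every explicit label for randomization says Week 0.
- *Taper starting at Week 0 (order B).* For: the Week 0 labels, and dispensing at that visit. Against: the arm-specific instruction under Screening.

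Neither A nor B fits all the text.

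**Step 2. Size under order A.** Let s be the net transient rise in the switch arm at Week 0, with no true difference at Week 8. Bias in favour of switch is:

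- change score: s
- ANCOVA on the Week 0 score: b × s, where b = r × SD(Week 8) / SD(Week 0)

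Inputs:

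- 30 per arm (section IV) and two-sided alpha 0.05 (Statistical Evaluation, part C).
- MADRS SD is not given. Part A pairs a difference of 4.9 with 60 subjects and power 0.80. A two-sided t-test with 30 per arm needs d = 0.736, so the implied SD is 4.9 / 0.736 = 6.7. This is only a lower anchor, because 4.9 is a drug-placebo difference.
- Assumed: Week 8 SD 6.7 to 9, Week 0 SD 5 to 9, correlation r 0.3 to 0.5.

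Slope b: minimum 0.3 × 6.7 / 9 = 0.223; maximum 0.5 × 9 / 5 = 0.90.

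Type I error comes from simulation with 40,000 trials per setting over six SD pairs and two correlations:

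| Rise s | ANCOVA bias (b × s) | ANCOVA type I error |
|---|---|---|
| 1 | 0.2 to 0.9 | 5 to 7% |
| 2 | 0.4 to 1.8 | 6 to 14% |
| 3 | 0.7 to 2.7 | 7 to 24% |

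For an unadjusted change score with Week 0 SD 6, Week 8 SD 9, r 0.3 to 0.5 and s = 2, bias is 2.0 points and type I error 13 to 15%. ANCOVA in the same setting gives 0.9 to 1.5 points and 7 to 11%.

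**Step 3. Partial offset.** If a share q of the quetiapine arm also changes antidepressant with the same rise, bias is b × s × (1 - q). For s = 3:

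- q = 10%: 0.669 × 0.9 = 0.60 to 2.70 × 0.9 = 2.43
- q = 25%: 0.669 × 0.75 = 0.50 to 2.70 × 0.75 = 2.02

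**Step 4. Pre-assignment MADRS as the covariate.** Simulated bias stays within 0.03 points and type I error is about 5%.

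**Step 5. Order B.** s = 0 at baseline, so there is no baseline bias.

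**The case against.** The best reply is that order B is what the plan means. Randomization is labelled Week 0 throughout. After screening, V.C speaks only of potential eligibility, criteria are rechecked at Week 0, and part B randomizes after eligibility is determined. The quetiapine instruction under Screening may merely describe what that arm may keep. This carries weight, and it is why the bias can be stated only conditionally. It is not conclusive, because V.B and V.D also speak of eligibility as settled at screening.

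Second, the taper is gradual precisely to limit discontinuation effects, and these subjects responded inadequately to the drug being withdrawn. Nothing in the documents shows that MADRS rises. This stands.

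Third, the 24% is a corner case: a 3-point rise, Week 0 SD 5, r = 0.5, and the same rise in everyone. With Week 8 SD 9 and a rise varying between subjects with SD 3, bias falls to 2.3 points and type I error to 18%. With SD 5 they are 1.8 points and 13%. This also stands.

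Fourth, randomization lists are held at one site, the monitoring plan is common to both sites, and monthly teleconferences cover screening issues. These lower the chance that the sites diverge, but none of them states the order.

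**Conclusion.** The inconsistency is in the text and should be fixed. Its effect on validity depends on order A, which is plausible but not required. Under order A the primary baseline is measured after randomization and altered mainly, though not only, in the switch arm: other-drug washout can occur in either arm, and some quetiapine subjects may change antidepressant. Any transient rise passes in full into a change score and by slope × rise into ANCOVA. The figures rest on assumed SDs, correlations and rise; at 1 point the effect is small.

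A reader might infer that the primary comparison is biased toward levomilnacipran. The documents do not support that: they do not establish order A, and they give neither the direction nor the size of any taper effect. A reader might also infer that switch-arm subjects who fail the taper will be lost from the ITT set, which requires study drug and a post-baseline rating. That could happen only under order A, and no failure rate is given, so no conclusion is drawn from it here.

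**What to change.** 1. State one order for both sites. The preferred order, all at Week 0, is eligibility recheck, baseline MADRS, randomization, then dispensing and start of the taper. State that the SSRI overlaps levomilnacipran during the taper, and have the investigators confirm that this is intended.
2. If assignment must precede the taper, define the primary baseline in both arms as the last MADRS before assignment, which is the screening score. Apply the entry criteria, including HAM-A, before assignment.

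Cost: wording in sections V.B and V.C, the Schedule of Events and part C. Both scales are already collected at screening and Week 0.

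Option 1 loses no precision. Under option 2 the baseline may be up to 4 weeks older. If its correlation with Week 8 falls from r0 to r1, the standard error changes by sqrt((1 - r1²) / (1 - r0²)):

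- 0.30 to 0.25: 1.015
- 0.30 to 0.20: 1.027
- 0.50 to 0.45: 1.031
- 0.50 to 0.40: 1.058

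That is an increase of about 1.5 to 6%, with the correlations assumed.
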